4.10.1 What is a SAE

A SAE is an *untoward* and *unexpected* occurrence that a research participant experiences which:

- i Results in death
- ii Is life threatening
- iii Requires hospitalisation or prolongation of existing hospitalisation
- iv Results in persistent or significant disability or incapacity
- v Consists of a congenital anomaly or birth defect.

4.10.2 Reporting a SAE:

An SAE must be recorded on the appropriate trial form by the clinician caring for the patient and reported locally immediately to the Principal Investigator at that centre. The Principal Investigator will then report the SAE to the Chief Investigator of the OSCAR trial, [name], within 3 working days of the event:

[name], Chief Investigator, OSCAR Trial Office, Kadoorie Centre for Critical Care Research and Education, John Radcliffe Hospital, [name]. [contact], [contact], Email: [contact].

[name] will give an opinion as to whether the event is:

- 'related' (resulted from administration of any of the research procedures), and
- 'unexpected' (the type of event is not listed in the protocol as an expected occurrence).

A confirmed, related, SAE will be submitted to a Main Research Ethics Committee within 15 days of the Chief Investigator becoming aware of the event using the NRES report of serious adverse event form.

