4.11 Expected events

Most known events related to artificial ventilation will occur equally in both groups. Exceptions that might occur more frequently in the HFOV group are:

- 1) Air trapping
- 2) Secondary effects of air trapping such as reduced carbon dioxide clearance.

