5 ORGANISATION

5.1 The Data Monitoring and Ethics Committee (DMEC)

The DMEC will comprise of a senior statistician, a senior clinician, and a senior trialist (Chair), see Appendix 6 for membership details.

Standard Operating Procedures for the DMEC:

- During the period of recruitment into the study, interim analyses of the proportion of patients alive at 30 days and analyses of deaths from all causes at 30 days will be supplied, in strict confidence, to the chairman of the DMEC, along with any other analyses that the committee may request.
- 2) In the light of these analyses, the DMEC will advise the Chairman of the Steering Committee if, in their view, the randomised comparisons have provided both (i) 'proof beyond reasonable doubt' that for all, or some, the treatment is clearly indicated or clearly contra-indicated and (ii) evidence that might reasonably be expected to materially influence future patient management.
- 3) Appropriate criteria of proof beyond reasonable doubt cannot be specified precisely, but the DMEC will work on the principle that a difference of at least 3 standard deviations in an interim analysis of a major outcome event may be needed to justify halting, or modifying, a study before the planned completed recruitment. These criteria have the practical advantage that the exact number of interim analyses would be of little importance, and so no fixed schedule is proposed.
- 4) Following a report from the DMEC, the Steering Committee will decide whether to modify entry to the study (or seek extra data). Unless this happens the Steering Committee and the collaborators will remain ignorant of the interim results.

- 5) Data relating to the safety of patients will be reviewed by the Chair of the DMEC once 50 patients have been randomised to the trial. The data reviewed will specifically relate to:
 - a) procedure related 'serious, unanticipated adverse events' (death or serious disability)
 - b) procedure related adverse events/ complications
 - c) deaths at 30 days (any cause)
- 6) The DMEC will meet to review at one year, or at 100 deaths, whichever occurs first. The DMEC will meet at intervals determined by the DMEC chair.

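### Sections 4.10.1, 4.10.2 and 4.11 do not fit together: read literally, a serious air-trapping event needs no SAE report

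*Protocol*

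**What the plan says.** Section 4.10.1 opens its definition with "A SAE is an *untoward* and *unexpected* occurrence that a research participant experiences which", followed by the seriousness criteria, one of which is "Is life threatening".

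Section 4.10.2 sets out the reporting chain. The treating clinician completes a form and tells the local Principal Investigator at once. The Principal Investigator reports to the Chief Investigator within 3 working days. The Chief Investigator then gives an opinion on relatedness and on expectedness, an event being unexpected if "the type of event is not listed in the protocol as an expected occurrence". The last step reads "A confirmed, related, SAE will be submitted to a Main Research Ethics Committee", with a 15-day limit.

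Section 4.11, on expected events, says most known ventilation-related events will be equally common in both groups. It continues "Exceptions that might occur more frequently in the HFOV group are" and names two items: air trapping, and "Secondary effects of air trapping such as reduced carbon dioxide clearance". Neither carries a severity limit.

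Section 5.1 gives the DMEC a separate route: "Data relating to the safety of patients will be reviewed by the Chair of the DMEC once 50 patients have been randomised". That review covers three things: "procedure related 'serious, unanticipated adverse events' (death or serious disability"), procedure-related adverse events or complications without any expectedness limit, and deaths at 30 days.

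**The concern.** Seriousness and expectedness normally do different jobs. Seriousness decides what is recorded and sent in; expectedness decides which of those reports need onward expedited submission. Section 4.10.1 merges the two, and section 4.11 then places the one named HFOV-specific harm on the expected side.

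At stake is the prompt reporting and causal assessment of serious events tied to the device under test. The trial is open, and section 5.13.2 says most units will not have used HFOV before. The gap is also one-sided: the only event types named as expected are those that might be more frequent in the HFOV arm. A count of SAEs by arm, built on this definition, would leave out the harm that the protocol itself singles out for HFOV.

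**Working it through.** No power or sample-size calculation bears on this point. The check is to apply the three sections in turn to a life-threatening air-trapping event.

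1. **Definition (4.10.1).** SAE = untoward AND unexpected AND meets at least one seriousness criterion.
2. **Seriousness (4.10.1).** The event is life-threatening, so a criterion is met.
3. **Expectedness (4.10.2).** Unexpected = event type not listed in the protocol. The test is by type, so severity does not enter.
4. **List (4.11).** Air trapping is listed by type, and so are its secondary effects. The event is therefore not unexpected.
5. **Result.** One of the three conditions in step 1 fails, so the event is not an SAE. The same holds for a fatal case.
6. **Consequence.** Each duty in 4.10.2 (the form, the immediate local report, the 3-working-day report, the Chief Investigator's opinion, the 15-day submission) attaches to an SAE. None is required for this event.

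The text also fails a consistency check. If every reported SAE is already unexpected by definition, the Chief Investigator's expectedness opinion can have only one answer. If that opinion is meant to matter, events not yet classed as unexpected must be reportable, which 4.10.1 excludes. Both cannot be followed as written. The submission sentence asks only for a confirmed, related SAE. It does not mention expectedness and relies on the definition to supply it.

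Other routes by which such an event could be seen:

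| Route | What it captures | Limit |
|---|---|---|
| Primary outcome (4.12) | A fatal case, as a death | No mechanism or attribution |
| DMEC chair's review, serious events (5.1, item 5a) | Procedure-related death or serious disability | Restricted to unanticipated events |
| DMEC chair's review, complications (5.1, item 5b) | Procedure-related events, expected or not | Named only for the review at 50 patients |
| DMEC requests and later meetings (5.1, items 1 and 6) | Whatever the committee asks for | Complications not named |
| Case report form (4.13) | Data for the outcomes and long-term follow-up | Fields not shown |

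The review at 50 patients falls at 50/802 = 6.2% of planned recruitment. For the remaining 802 − 50 = 752 patients, no complication review is scheduled by name.

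**The case against.** The strongest reply is that the reporting chain shows what was intended. The clinician files, the Principal Investigator forwards, and only then does the Chief Investigator rule on expectedness, so expectedness was evidently to be settled centrally after filing. That is a plausible reading of intent, and a clinician might well send the form in. It does not repair the text: a site that applies 4.10.1 as written would not file, and the central judgement would not take place.

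A second reply is that safety oversight does not rest on SAE forms alone. This stands, and it rules out several stronger conclusions that a reader might draw:

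- **That the arms cannot be compared on this harm.** The case report form fields are not shown, and tabulation of adverse events is commonly left to the analysis plan. Air trapping may be recorded there.
- **That the DMEC has nothing to work with after 50 patients.** Section 5.1 lets it request any analysis and provides for a meeting at one year or 100 deaths, whichever comes first, and at intervals set by its chair thereafter. Supplying complications at 50 patients also implies that they are collected in some form.
- **That the trial measures no harm.** Mortality at several time points, non-pulmonary organ failures, ventilator-free days and one-year pulmonary function would all register net harm.
- **That HFOV complications appear nowhere else.** Section 4.20 refers to HFOV-specific complications as a reason for a change of ventilation, though it creates no duty to report them.
- **That the protocol predicts more air trapping with HFOV.** It says only that this might happen.

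A third reply concerns burden. Section 4.16 originally assumed a control-group mortality of 45%. If seriousness alone defined an SAE, every death and prolonged stay would generate a form. That is a fair objection, and the remedy has to meet it.

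**Conclusion.** The three sections conflict and need to be reconciled. Under their literal wording, a serious air-trapping event, or a serious secondary effect of one, falls outside SAE reporting whatever its severity, and the Chief Investigator's expectedness judgement is redundant. The loss is confined to expedited reporting and attribution of serious device-related events, together with the absence of any complication review scheduled by name after 50 patients. The primary outcome is not affected, and fatal cases are still counted as deaths.

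No number of missed events can be given, because the protocol states no rate of air trapping. The conclusion does not depend on such a rate. It rests on reading 4.10.1 as a filing rule, which is how its wording presents it. If sites in practice filed every serious event and left expectedness to the Chief Investigator, the loss would be smaller, but the text would still need correcting. This is a cheap safety improvement that should be made.

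**What to change.** 1. In 4.10.1, remove unexpectedness from the SAE definition.
2. In 4.10.2, make related and unexpected together the test for ethics-committee submission, and say so in the submission sentence, which now mentions relatedness only. The Chief Investigator's expectedness opinion then has a purpose.
3. To limit burden, exempt from expedited forms those serious events of the underlying illness that are already captured as outcomes. State explicitly that the events listed in 4.11 are not exempt.
4. Record the 4.11 events in both arms on the case report form, and list them by arm at each DMEC review rather than only at 50 patients.

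The cost is a short amendment, a case report form field and some additional SAE forms. The exemption must be worded carefully so that it does not reopen the same gap. The change concerns reporting only and leaves patient management as it is.

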4.11 Expected events

Most known events related to artificial ventilation will occur equally in both groups. Exceptions that might occur more frequently in the HFOV group are:

- 1) Air trapping
- 2) Secondary effects of air trapping such as reduced carbon dioxide clearance.

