It eventually became apparent that high frequency jet ventilation and high frequency positive pressure ventilation probably had no special properties and conformed to the conventional, convective, model of gas exchange [32]. However, it also became clear that carbon dioxide clearance could be achieved with HFOV in animals [33] and humans [34] with tidal volumes that were half the anatomical dead space or less. There are many theories to explain this phenomenon. All of them reject the simple anatomical (series) dead space concept, and assume there is no sharp cut-off between dead space and alveolar gas, and some form of mixing takes place. The most likely mechanism, termed "convective streaming", is that the interaction of the gas-airway wall friction and the asymmetrical inspiratory-expiratory flow profiles lead to a net inward movement of gas in the core of the large airways and a net outward movement near the wall [35]. These theories have been extensively reviewed [36, 37].

As tidal volumes during HFOV are very small, the peak and mean pressures generated in the lungs during artificial ventilation are correspondingly modest. Thus HFOV would seem an ideal technique to ventilate patients at risk from pressure-induced lung damage ("barotrauma") such as infants with the (infant) respiratory distress syndrome. This was the rationale behind the early trials of HFOV in infants.

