2.2.4 Trials of HFOV in adults

We undertook a systematic review of HFOV in patients with ARDS and ALI in July 2006 to update the 2004 Cochrane review [6]. Amongst the 319 papers identified, there were only two randomised controlled trials of HFOV in adults. Other uncontrolled and retrospective studies of HFOV in patients with ARDS and ALI identified in the systematic review are listed in Appendix 2.

The first and largest randomised controlled trial was published in 2002 [9]. Recruitment took place between October 1997 and December 2000 in 13 University-affiliated medical centres in the USA and Canada. A total of 148 patients were recruited. The entry criteria were the ARDS Consensus criteria, a PEEP of \geq 10cmH₂O, and a predicted 6 month survival of 50% or greater. They initially set the HFOV ventilator to a frequency of 5Hz (breaths per second) and a mean pressure 5cmH₂O above the mean airway pressure on conventional ventilation, and the amplitude to "visible chest wall movement". The conventional ventilation group were treated with pressure-controlled ventilation to a maximum tidal volume of 10ml kg⁻¹. The HFOV group had better oxygen exchange as measured by PaO₂/FiO₂ ratios, most notably in the first 24 hours of HFOV, though when corrected for the difference in mean airway pressure (which increases oxygen exchange) using the oxygenation Index (OI) this difference disappeared. Although more deaths were seen in the control group, this was not statistically significant (see figure 1 below).

The second study was published in 2005 [10]. Recruitment took place in 4 Universityaffiliated medical centres in London, Cardiff, Mainz and Paris between October 1997 and March 2001. The entry criteria and HFOV management were virtually identical to the 2002 study. A total of 61 patients were recruited. This study showed a beneficial effect of HFOV on oxygenation, even when airway pressures were taken into account. There was an excess of deaths in the HFOV arm which was not statistically significant.

The results for 30 day mortality from both studies have been combined in the forest plot in figure 1. There is no statistically significant benefit for HFOV seen.

Study	HFOV Died/N	Control Died/N	OR (rand 95% C		OR (random) 95% Cl
Derdak 2002 Bollen 2005	28/75 16/37	38/73 8/24		58.90 41.10	0.55 [0.28, 1.06] 1.52 [0.52, 4.44]

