4.9 Treatment

4.9.1 Clinical management of the patients in the high frequency oscillatory ventilation arm

Clinicians will be trained to adjust the ventilator according to a protocol derived from guidelines which have been used successfully at Addenbrookes Hospital ICU (Cambridge) and the University Hospitals, Birmingham, for 5 years. It is virtually identical to the protocols used in the two published randomised controlled trials (MOAT and eMOAT). The flow diagram is shown on the next page.

Continue over/...

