	point of measurement if HFOV			
	ended within the first 24h; or			
	b) HFOV-related complications.			
Secondary outcomes	30 day mortality, relationship	HFOV oxygenation and/or		30 day mortality.
	between endpoint outcomes and	ventilatory failure, duration of		
	HFOV treatment response.	HFOV, ICU mortality, complications.		
Primary outcome results	Median PaO ₂ /FiO ₂ ratio from	Cardiac output decreased	All patients improved	HFOV caused significant increases in
	baseline to 24 hours 95(62-129) to	significantly immediately after	after initation of HFOV.	PaO ₂ /FiO ₂ ratio and significant reductions
	165 (88-225) mmHg.	starting HFOV, and remained		in the oxygenation index.
	HFOC-related complications:	lower than the baseline value		
	1/48.	throughout the study (ns).		
Secondary outcome results	30 day mortality	Complications		30 day mortality
	HFOV: 18/42	HFOV: 6		HFOV: 9/17
		ICU mortality		Alive no mechanical ventilation
		HFOV: 16		HFOV: 3/17
		Hospital mortality		
		HFOV: 16		
Intention to treat analysis	Not applicable		Not applicable	Yes

OSCAR TRIAL PROTOCOL c) Prospective trials of HFOV without usual care control group

First author	Ferguson [70]	Papazian [71]	
Publication year	2005	2005	
Aim of HFOV	Primary treatment	Primary treatment	
Patient population	Adults with early ARDS	Adults with severe ARDS	
Study type	Prospective multi-centre single intervention pilot study	Prospective comparative randomised study	
Setting	Canadian ICU, UK ICU and French ICU	French Medical ICU	
Age limits	18 – 74	18 or older	
Inclusions	Endotracheal intubation and mechanical ventilation. Presence of one or more risk factors for ARDS. Bilateral infiltrates as seen on frontal chest radiograph. PaO_2/FiO_2 ratio <200mmHg.	PaO₂/FiO₂ ratio ≤150mm Hg while on PEEP ≥5cmH₂O, bilateral radiographic pulmonary infiltrates, and pulmonary artery occlusion pressure of ≤18mmHg.	

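### The HFOV harm profile in sections 2.2.2 and 4.11 does not fit the protocol's own evidence, and the safety rules leave non-fatal air-leak and haemodynamic events open to under-reporting by arm

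*Protocol*

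**What the plan says.** **Pressure.** Section 2.2.2 says that, because HFOV tidal volumes are very small, "the peak and mean pressures generated in the lungs during artificial ventilation are correspondingly modest". Section 2.2.4 says the larger adult trial started HFOV at "a mean pressure 5cmH₂O above the mean airway pressure on conventional ventilation" and that the second trial managed HFOV in almost the same way. Appendix 2(a) tabulates the 5 cmH₂O increment for both. Of OSCAR's own HFOV algorithm, section 4.9.1 says: "It is virtually identical to the protocols used in the two published randomised controlled trials".

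**Harms.** Section 4.11, headed as the list of expected events, opens with "Most known events related to artificial ventilation will occur equally in both groups". It then gives two exceptions that might be more frequent with HFOV: air trapping, and "Secondary effects of air trapping such as reduced carbon dioxide clearance". For a 24-patient rescue series, Appendix 2(b) begins its result with "Cardiac output decreased". It describes the fall on starting HFOV as significant and says output stayed below baseline throughout, with (ns) at the end. Appendix 2(a) and 2(c) list air leak, mucus plugging or obstruction, and vasopressor need among the outcomes of comparative HFOV studies.

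**Reporting.** Section 4.10.1 makes being unexpected part of the definition of an SAE. Section 4.10.2 treats an event type as unexpected if the protocol does not list it as expected. At 50 patients, section 5.1 gives the DMEC chair procedure-related serious unanticipated events, "procedure related adverse events/ complications", and 30-day deaths from any cause.

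**The concern.** The protocol's account of which harms may differ by arm is narrower than the evidence it cites. That account also has a function, because section 4.11 is what decides whether an event is expected. If known ventilation events as a class are expected, a serious pneumothorax or a serious haemodynamic collapse on the ventilator may never enter SAE reporting.

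The 50-patient review does not close the gap. Apart from deaths, it sees only events that someone has tied to the procedure. The trial is open (section 4.1), so that judgement is made by staff who know the arm. In a ventilated ARDS patient such events have obvious alternative explanations. At stake is the by-arm comparison of non-fatal air leak and shorter haemodynamic episodes, not the primary mortality analysis.

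**Working it through.** The protocol states no figure to reproduce here, so the check is mainly textual.

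**1. Is the pressure description consistent?** Section 2.2.2 calls both peak and mean pressures modest. Section 2.2.4 and Appendix 2(a) give a starting mean pressure 5 cmH₂O above conventional. Section 2.2.4 adds that the larger trial's oxygenation advantage disappeared once the difference in mean airway pressure was allowed for, so the arms did differ in that trial. Section 4.9.1 links those settings to OSCAR. OSCAR's own flow diagram is not in the text available, so the 5 cmH₂O increment is inferred for OSCAR, not read from its algorithm.

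**2. Is the list in 4.11 consistent with Appendix 2?** It contains neither haemodynamic compromise nor air leak. Appendix 2(b) reports a cardiac output fall. Appendix 2(a) and 2(c) show that earlier investigators thought air leak, mucus plugging and vasopressor need worth measuring. Section 4.4 excludes recent lung biopsy or resection under the heading of patients for whom HFOV might be hazardous. None of this shows a difference between arms. It does show that the list omits candidates which the protocol itself had before it.

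**3. How do 4.10 and 4.11 interact?** Two readings are possible.
- *Only the two numbered items are listed.* Serious air leak and haemodynamic events are then unlisted, so unexpected and reportable.
- *The opening sentence lists the class.* The two items are exceptions to equal frequency, not exceptions to being expected. On this reading the whole class of known ventilation events is expected and falls outside the SAE definition.

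The text does not choose between them.

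**4. Which routes capture what?**

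| Event | SAE route (4.10–4.11) | Outcome data (4.12, 4.13) | 50-patient review (5.1) |
|---|---|---|---|
| Death | Depends on the reading | Yes | Yes, any cause |
| Sustained circulatory failure | Depends on the reading | Yes, as non-pulmonary organ failure | Only if judged procedure-related |
| Shorter haemodynamic episode | Depends on the reading, if serious | Not named | Only if judged procedure-related |
| Non-fatal air leak | Depends on the reading, if serious | Not named (a pulmonary event) | Only if judged procedure-related |

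Section 4.20 also returns patients with HFOV-specific complications to conventional ventilation without defining those complications, so it supplies no list either.

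**5. Scale.** With 1:1 allocation (section 3.3), 50/2 = 25 patients are on HFOV at the first safety review, against 401 at the end. The protocol gives no event rates. As an assumption, take control rates p₀ from 5% to 30% and a 10-point excess, p₁ = p₀ + 0.10, with full capture in both arms and two-sided 5% testing. Let p̄ be the mean of p₀ and p₁.

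Power = Φ[(0.10 − 1.96·SE₀)/SE₁], where SE₀ = √(2p̄(1−p̄)/n) and SE₁ = √((p₀(1−p₀)+p₁(1−p₁))/n).

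- p₀ = 5%, n = 25: (0.10 − 1.96×0.0849)/0.0837 = −0.79, giving 21%.
- p₀ = 30%, n = 401: (0.10 − 1.96×0.0337)/0.0335 = 1.01, giving 84.5%.

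| p₀ → p₁ | 25 per arm | 401 per arm |
|---|---|---|
| 5% → 15% | 21% | 99.7% |
| 10% → 20% | 16% | 98% |
| 20% → 30% | 12.5% | 91% |
| 30% → 40% | 11% | 84.5% |

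The 50-patient table can show only gross imbalance. Complete capture pays off in the cumulative by-arm counts at later reviews.

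**The case against.** Several points on the other side stand.

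- **Organ failure and deaths are captured.** Non-pulmonary organ failure is a secondary outcome (4.12) collected in a standardised way (4.13), whatever the judged cause. A reader might infer that haemodynamic harm would surface only as deaths. The protocol does not support that.
- **The DMEC is not confined to the 50-patient list.** Section 5.1 lets it request other analyses and provides for later meetings. Someone must still ask, and the data must have been collected.
- **The evidence of harm is weak.** A reader might infer that the protocol shows HFOV to cause more circulatory compromise or air leak. It does not. The cardiac output entry is one uncontrolled rescue series, and it says both significant and (ns). The other events are listed as outcomes, with no result showing a difference by arm.
- **Section 4.11 is hedged.** It says most events, not all, and covers secondary effects of air trapping. Section 2.2.2 is background to the infant trials, gives no pressure values, and is not cited by 4.11.
- **A reader might infer that OSCAR's algorithm itself raises mean pressure by 5 cmH₂O.** Section 4.9.1 makes that plausible, but without the flow diagram it is not established.
- **Adding the events to 4.11 and nothing more could backfire.** Under 4.10.2, a listed event becomes expected and so leaves SAE reporting. This is correct and shapes the fix.
- **The CRF is not shown,** so missing fields cannot be asserted. The sentence at issue is also absent from the staff summary in Appendix 9, so its effect on bedside reporting is uncertain.

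These points narrow the consequence. They do not resolve the inconsistency or the ambiguity between 4.10 and 4.11.

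**Conclusion.** The point holds in a limited form. Sections 2.2.2 and 4.11 are inconsistent with sections 2.2.4 and 4.9.1 and Appendix 2(a), and fit poorly with Appendix 2(b) and 2(c). The practical defect is that serious air-leak and haemodynamic events can be read as expected and so not reported, while the 50-patient review depends on attribution by unblinded staff for everything except death.

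The gap is confined to non-fatal air leak and shorter haemodynamic episodes. It does not touch the primary outcome, and no excess harm is demonstrated. The conclusion assumes that OSCAR's undisplayed flow diagram follows the earlier trials, as 4.9.1 says, and that the CRF does not already record these events in both arms. If the CRF does record them, what remains is the wording and the DMEC table. The change is worth making because it is cheap and because the cumulative by-arm comparison cannot be recovered later if the events were never recorded.

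**What to change.** 1. Reconcile sections 2.2.2 and 4.11 with sections 2.2.4 and 4.9.1 and Appendix 2, and clarify the (ns) mark on the cardiac output entry.
2. State that haemodynamic compromise and air leak may differ by arm. In the same place, state that neither this nor the first sentence of 4.11 exempts serious cases from SAE reporting under 4.10.
3. Where the CRF does not already do so, record air leak, haemodynamic compromise and vasopressor use in both arms, regardless of judged relatedness.
4. Give the DMEC by-arm counts of these, together with organ failures, at 50 patients and at each later review.

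The cost is a short protocol and CRF amendment, a few routinely charted items and one more DMEC table. No ventilator setting or clinical rule is judged or changed.
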